##### **9.4.9.2 Restricted Therapy and Medications**

Patients with a previous orbital irradiation, orbital decompression or strabismus surgery or who have a planned orbital irradiation or surgery for TED during this trial are not eligible for the trial. In addition, oral corticosteroids, immunosuppressive agents, investigational agents and illicit drug/alcohol use are restricted, as shown in Table 9.1.

**Table 9.1      Restricted Medications and Therapies**

Medication/Therapy	Restricted Dose or Time Period
Orbital irradiation, orbital decompression or strabismus surgery	Any history or planned irradiation or surgery during the trial.
Steroids	Steroids (intravenous or oral) and steroid eye drops within 3 weeks prior to Screening. Systemic steroid use (intravenous or oral) and steroid eye drops are not to be initiated during the trial; however, topical and inhaled steroids are allowed. Steroids for the treatment of infusion reaction are allowed.
Non-steroid eye drops	Non-steroid drops, such as saline or methylcellulose, antihistamines and vasoconstrictors are allowed but must not be used on the day of a clinic visit.
Rituximab (Rituxan® or MabThera®)	Within 12 months prior to the first infusion of trial drug and during the trial.
Tocilizumab (Actemra® or Roactemra®)	Within 6 months prior to the first infusion of trial drug and during the trial.
TEPEZZA	Any previous treatment with TEPEZZA or teprotumumab, including, but not limited to enrollment in this trial or participation in a prior TEPEZZA trial or program.
Monoclonal antibody	Within 3 months prior to Screening.
Non-steroid immunosuppressive agent (other than rituximab or tocilizumab)	Within 3 months prior to the first infusion of trial drug and during the trial.
Investigational agent	Within 60 days or 5 half-lives, whichever is longer prior to Screening or anticipated use during the trial.
Neonatal Fc receptor (FcRn) agents	During the trial.
Illicit drug/alcohol use	History of abuse within the past 2 years or abuse during the trial.

It is recommended to avoid ototoxic medications and medications that may cause muscle spasm/cramps during the trial.

All concomitant treatment (for TED and other conditions) must be documented in the eCRF.

#### **9.4.10 Treatment Compliance**

The Principal Investigator is responsible for ensuring that dosing is administered in compliance with the protocol. Delegation of this task must be clearly documented and approved by the Investigator.

All infusions of trial drug will be administered at the clinic or infusion center under adequate healthcare professional supervision. Calculated trial drug dose and start and stop times of the infusions will be recorded in the eCRF.

An inventory of the trial drug supplies will be performed by the authorized site designee and recorded onto the Drug Accountability Log in the patient's source document records or equivalent.

## 9.5 Efficacy, Pharmacokinetic, Safety and **CCI** Variables

The Schedule of Assessments is provided in Section 2.1.

### 9.5.1 Efficacy Variables

At the Baseline (Day 1) Visit, the "study eye" (i.e., the eye with most significant proptosis) will be identified. If both eyes are affected equally, the Investigator will choose the "study eye." Both eyes will be assessed for efficacy, but the study eye will be used to assess the primary efficacy endpoint.

Efficacy will be assessed by proptosis (measured as proptosis evaluation of the Clinical Measures of Severity using a Hertel instrument provided by the Sponsor for consistency in measurement), **CCI**

**CCI** , quality of life (using the GO-QoL questionnaire) and, **CCI**

#### 9.5.1.1 Proptosis

Proptosis assessments will be performed using a Hertel exophthalmometer provided by the Sponsor for consistency in measurement and (except when strictly unavoidable), the same Hertel instrument and same observer should be used at each evaluation for the duration of the trial. Additionally, the same intercanthal distance must be used on each occasion. Instructions for the measurement of proptosis are included in Appendix 17.4.

Proptosis will be measured for each eye at Screening, Day 1 and Weeks 3, 6, 12, 18 and 24 (or premature withdrawal 1 [PW1]) (all patients) and Weeks 27, 30, 36, 42 and 48 (or premature withdrawal 2 [PW2]) (proptosis non-responders who elect to receive open-label TEPEZZA) (see Section 2.1). Patients who have a >2-mm decrease in proptosis from Screening to Baseline in the study eye are not eligible for randomization. Measurements will be recorded on the Clinical Measures of Severity eCRF under exophthalmos.

#### 9.5.1.2 **CCI**

Based on the European Group on Graves' Ophthalmopathy Consensus Statement, **CCI**

**CCI**

**CCI**

## CCI

Table 9.2 Clinical Measures of Severity

### 9.5.1.3 CCI

CCI [REDACTED] on Day 1 and Weeks 3, 6, 12, 18 and 24 (or PW1) (all patients) and at Weeks 27, 30, 36, 42 and 48 (or PW2) (proptosis non-responders who elect to receive open-label TEPEZZA) (see Section 2.1). Patients will be asked to CCI [REDACTED]

CCI

CCI [REDACTED] is included in Appendix 17.2.

CCI [REDACTED]

CCI [REDACTED]

Section 2.1

CCI [REDACTED]

### 9.5.1.5 Clinical Activity Score

The CAS assessment (Table 9.3) will be completed at Screening, Day 1 and Weeks 12 and 24 (or PW1) (all patients) and Weeks 36 and 48 (or PW2) (proptosis non-responders who elect to receive open-label TEPEZZA) using the 7-item European Group on Graves' Ophthalmopathy amended CAS (see Section 2.1).

Table 9.3

**CCI**

Item^1 Description

**CCI**

Each item is scored (CCI [REDACTED]) and scores for each item are summed for total score.

To promote consistency in data collection across sites, all Investigators will be provided with training and copies of the Clinical Manifestations chapter in *Graves' Orbitopathy: A Multidisciplinary Approach – Questions and Answers*. Except when strictly unavoidable, the same observer should conduct each CAS evaluation for the duration of the trial.

9.5.1.6 **CCI**

**CCI**

The CCI [REDACTED]  
CCI [REDACTED]  
version of the questionnaire is included in [Appendix 17.5](#).

The English

9.5.2 **Pharmacokinetic Measurements**

Blood samples will be collected in 5-mL serum separator collection tubes to evaluate PK at the following visits: pre- and post-infusion on Day 1, Weeks 3 and 12 of the double-masked Treatment Period (all patients) and at Weeks 24, 27 and 36 (non-responders who elect to receive open-label TEPEZZA); a single sample will also be collected at Week 24 (or PW1) of the double-masked Treatment Period (proptosis responders and proptosis non-responders who elect not to receive open-label TEPEZZA) and Week 48 (or PW2) of the open-label Treatment Period (non-responders who elect to receive open-label TEPEZZA) (see [Section 2.1](#)).

PK samples will be collected, processed and stored at  $\geq 70^{\circ}\text{C}$  at the site until shipment to the central laboratory (CCI [REDACTED]). The central laboratory will store the samples at  $\geq 70^{\circ}\text{C}$  until shipment to the appropriate laboratory for testing.

Instructions for processing, handling, storing and shipping of PK samples will be detailed in a laboratory manual that will be provided to each site prior to site initiation.

### 9.5.3 Safety Variables

Safety will be assessed via AE (including AESIs) and concomitant medication use monitoring, immunogenicity testing, best-corrected visual acuity, vital signs, clinical safety laboratory evaluations (complete blood count and fasting chemistry [including thyroid panel and HbA1c]) and pregnancy testing (if applicable).

#### 9.5.3.1 Adverse Events

##### 9.5.3.1.1 Definitions

###### 9.5.3.1.1.1 Adverse Event Definition

According to ICH, an AE is any untoward medical occurrence in a patient or clinical investigation subject administered a pharmaceutical product and that does not necessarily have a causal relationship with this treatment. An AE can, therefore, be any unfavorable and unintended sign (including an abnormal laboratory finding), symptom or disease temporally associated with the use of a medicinal (investigational) product, whether or not considered related to the medicinal (investigational) product.

Pre-existing conditions that worsen during the trial are to be reported as AEs. New findings reported from the on-trial visual acuity assessments will not be reported as AEs if, according to the Investigator, the abnormalities are related to TED and not considered related to the trial drug.

Unchanged, chronic conditions are NOT considered AEs and should not be recorded on the AE pages of the eCRF unless there is a clear exacerbation of a chronic condition.

Disease progression can be considered as a worsening of a patient's condition attributable to the disease for which the trial drug is being studied (i.e., TED) and may be an increase in the severity of the disease under study and/or increase in the symptoms of the disease. The development of worsening proptosis may be considered as disease progression and not an AE. Events that are unequivocally due to disease progression should only be reported as AEs if they fulfill any of the SAE criteria or are the reason for discontinuation of trial drug.

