###### 9.5.3.1.1.2 Serious Adverse Event Definition

A treatment-emergent adverse event (TEAE), Baseline event, or suspected adverse reaction is considered serious if, in the view of either the Investigator or Sponsor, it results in any of the following outcomes:

- Death. This includes any death that occurs during the conduct of a clinical trial, including deaths that appear to be completely unrelated to the trial drug (e.g., due to car accident).
- Life-threatening adverse experience. An AE or suspected adverse reaction is considered life-threatening if, in the view of either the Investigator or the Sponsor, its occurrence places the patient at immediate risk of death. It does not include an AE or suspected adverse reaction that, had it occurred in a more severe form, might have caused death.

- Persistent or significant disability or incapacity.
- Inpatient hospitalization or prolongation of an existing hospitalization.
- Congenital anomaly or birth defect.
- Another medically important event that, according to appropriate medical judgment, may require medical or surgical intervention to prevent 1 of the outcomes listed above.

Surgical procedures or other therapeutic interventions themselves are not AEs, but the condition for which the surgery intervention is required is an AE and should be documented accordingly.

Elective surgeries that require hospitalization and treatment received at an emergency room or similar facility will not be considered as SAEs unless 1 of the definitions of an SAE listed above is met.

In addition, a hospitalization for planned procedures is not considered an AE unless the hospitalization becomes prolonged. An emergency room visit less than 24 hours in duration is not considered a hospitalization.

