#### 9.5.3.1.5 Reporting and Documenting Serious Adverse Events

All SAEs beginning with the time of signing of the ICF and continuing until 30 days after trial discharge must be reported. The following steps will be taken to report promptly and document accurately any SAE, whether or not it appears to be related to trial drug:

1. Report the SAE to the Sponsor by **entering the information in the eCRF within 24 hours** after becoming aware that a patient has experienced an SAE. If unable to access the eCRF, the event must be reported by submitting the completed SAE form by email to [[contact]](mailto:[contact]), or via fax **within 24 hours** after becoming aware that a patient has experienced an SAE (see [Appendix 17.1](#) for contact information).
2. Perform appropriate diagnostic tests and therapeutic measures, and submit all follow-up substantiating data, such as diagnostic test reports, hospital discharge summaries and autopsy report to the Sponsor's representative.
3. Respond in a timely manner to any queries from Sponsor regarding the SAE.
4. Conduct appropriate consultation and follow-up evaluation until the SAE is resolved, stabilized, or otherwise explained by the Investigator.
5. Review each SAE report and evaluate the relationship of the SAE to trial treatment. The Sponsor will determine whether the SAE is unexpected in nature.
6. The Investigator must report to the IRB all AEs or SAEs that meet the criteria for Unanticipated Problems Involving Risks to Human Subjects or Others.

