#### **9.5.3.6 Visual Acuity**

Best-corrected visual acuity will be assessed at Screening, Day 1 and Weeks 6, 12, 18, and 24 (or PW1) and at Weeks 30, 36, 42 and 48 (or PW2) (non-responders who elect to receive open-label TEPEZZA) (see Section 2.1).

If significant abnormalities are noted compared with previous visits, including a loss of 2 lines or more of vision or other abnormalities not otherwise specified but of concern to the ophthalmologist, further investigations of visual function will be conducted according to the ophthalmologist's decision.

New findings reported from on-trial visual acuity assessments will not be reported as AEs if, according to the Investigator, the abnormalities are unequivocally due to disease progression and should only be reported as AEs if they fulfill any of the SAE criteria or are the reason for discontinuation of trial drug.

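### Protocol 9.5.3.1.1.1 and 9.5.3.6 set different thresholds for leaving new visual-acuity findings off the AE form, and the acuity sentence in 9.5.3.1.1.1 omits the serious/discontinuation exception

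*Protocol*

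**What the plan says.** Two places in the protocol govern new findings from the on-trial acuity assessments.

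- **Section 9.5.3.1.1.1 (Adverse Event Definition), acuity sentence.** A new finding is not an AE if, according to the Investigator, "the abnormalities are related to TED and not considered related to the trial drug". The sentence has no threshold of certainty and no exception for serious events or for events that stop treatment.
- **Section 9.5.3.6 (Visual Acuity).** The exemption applies when the Investigator judges that "the abnormalities are unequivocally due to disease progression and should only be reported as AEs if they fulfill any of the SAE criteria". Stopping trial drug because of the finding is a second ground for reporting.

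Three other statements in 9.5.3.1.1.1 bear on the matter. Just before the acuity sentence: "Pre-existing conditions that worsen during the trial are to be reported as AEs". In the last paragraph, a definition: "Disease progression can be considered as a worsening of a patient's condition attributable to the disease for which the trial drug is being studied". The closing sentence then reads: "Events that are unequivocally due to disease progression should only be reported as AEs if they fulfill any of the SAE criteria", again with discontinuation as a second ground for reporting.

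**The concern.** The two sentences cover the same data and rest on different judgements. One asks whether the finding is attributable to TED and not to the drug. The other asks whether progression is beyond doubt the cause. A site can comply with either and record the same event differently.

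The incidence of TEAEs, SAEs and TEAEs leading to discontinuation is a named safety endpoint (Protocol 9.6.1.4), so the rule decides what enters the AE tables. Entry requires stable, inactive disease (9.3.1), and recent loss of acuity from optic neuropathy is an exclusion (9.3.2). New acuity loss on trial is therefore informative. The background (7.1.1) lists several ways in which TED itself threatens sight, so attribution to TED is easy to make.

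The acuity sentence also makes causality a condition for being an AE at all, whereas the general definition at the start of 9.5.3.1.1.1 applies regardless of causality. Section 9.5.3.1.4 gives the causality assessment to the Investigator and the Sponsor. Under the acuity sentence the Investigator's view alone settles the matter, and the event is not put to the Sponsor as an AE.

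**Working it through.** There is no figure in the plan to reproduce. The check is to run each type of new acuity finding through both sections. In every row the Investigator judges the finding related to TED and not to trial drug.

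| Case | 9.5.3.1.1.1, acuity sentence | 9.5.3.1.1.1, closing sentence | 9.5.3.6 | Result |
|---|---|---|---|---|
| 1. Non-serious, drug continued, progression not unequivocal | Exempt | Does not apply | Not exempt | Conflict |
| 2. Non-serious, drug continued, progression unequivocal | Exempt | Exempt | Exempt | Agree |
| 3. Serious or causing discontinuation, progression unequivocal | Exempt if read alone | Report | Report | Agree once the section is read whole |
| 4. Serious or causing discontinuation, progression not unequivocal | Exempt | Does not apply | Report | Ambiguous |

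Case 1 is the main finding. It turns on the step from *related to TED* to *unequivocally due to progression*.

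For case 4, the other safety sections need to be checked.

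1. Section 9.5.3.1.5 points towards reporting: "All SAEs beginning with the time of signing of the ICF and continuing until 30 days after trial discharge must be reported", and its steps apply to "any SAE, whether or not it appears to be related to trial drug".
2. Section 9.5.3.1.1.2, however, limits what can be an SAE: "A treatment-emergent adverse event (TEAE), Baseline event, or suspected adverse reaction is considered serious if" one of the listed outcomes follows. A new finding that the acuity sentence has ruled not to be an AE, and that is judged unrelated to the drug, does not clearly fit any of the three.
3. If the loss is non-serious but leads to stopping the drug, 9.5.3.1.5 does not apply, because it concerns SAEs only.

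So case 4 is not settled by the SAE sections.

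**Exposure to the conflict.** Acuity is assessed after baseline at Weeks 6, 12, 18 and 24 in all patients and at Weeks 30, 36, 42 and 48 in open-label patients (9.5.3.6). These are occasions on which the rule applies, not expected events.

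**Weight of one patient.** With the planned 38 and 19 patients (9.6.7), one patient with an event is 1/38 = 2.6% of the TEPEZZA group and 1/19 = 5.3% of the placebo group. That holds for any event in this trial. It is not an estimate of how many findings would be recorded differently.

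**The case against.** The strongest reply is that this is a drafting slip with little consequence. Section 9.5.3.1.1.1 should be read whole. It defines progression as worsening attributable to TED, so a TED-related acuity loss is progression, and the closing sentence then supplies the missing exception. What remains is one word, *unequivocally*. Much of this stands: it removes case 3 and narrows case 4. It does not remove case 1, because a loss can be attributed to TED without that attribution being beyond doubt.

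A second reply is that the vision data are not lost. Best-corrected visual acuity is its own safety endpoint, with shift tables by eye, visit and treatment group (SAP 10.4), and supporting raw data are listed (SAP section 5). Section 9.5.3.6 also provides for further investigation, at the ophthalmologist's decision, after a loss of 2 lines or more. This stands too: an unreported finding is missing from the AE tables, not from the database. But the shift tables are not a full substitute. SAP 10.4 classes 20/12 to 20/40 as normal, so a fall from 20/20 to 20/40 shows no shift, and the tables carry no seriousness, causality or discontinuation.

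A reader might infer three stronger points, which the documents do not support.

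- *Serious vision loss attributed to TED is never an AE under 9.5.3.1.1.1.* The closing sentence of that section reports serious progression events, and 9.5.3.1.5 requires SAEs to be reported whatever their cause. Optic neuropathy with hospital admission is also a diagnosis with a serious outcome, not merely a finding from an acuity assessment.
- *Events drop out of expedited reporting to health authorities.* Section 9.4.8 describes such submission for unexpected SAEs that are drug-related. The acuity sentence reaches only findings judged not drug-related.
- *The treatment comparison is biased.* Investigators are masked, and nothing in the documents suggests that inconsistent site practice would favour one arm.

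**Conclusion.** The concern holds as an inconsistency in AE reporting. The two sections use different thresholds for exempting new acuity findings, and the acuity sentence in 9.5.3.1.1.1 lacks the exception found in 9.5.3.6 and at the end of its own section. Non-serious losses attributed to TED but not unequivocally to progression are treated in opposite ways. Serious or discontinuation-causing losses of the same kind are ambiguous, and 9.5.3.1.1.2 and 9.5.3.1.5 do not clearly settle them.

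The consequence is that ocular TEAE counts can depend on which section a site follows. The documents give no rate of new acuity findings, so the number affected cannot be estimated.

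The conclusion rests on two assumptions. First, a new acuity loss outside an exemption counts as an AE under the general definition. Second, Investigators will sometimes attribute a loss to TED without being certain that it is progression. If they never did, cases 1 and 4 would be empty and the two sections would agree in practice.

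**What to change.** Reconcile the passages so that one rule applies. Delete the acuity sentence in 9.5.3.1.1.1 and put a cross-reference to 9.5.3.6 in its place. A new acuity finding is then exempt only when unequivocally due to progression, and is still reported if it meets an SAE criterion or is why trial drug was stopped. This introduces no new policy, since 9.5.3.6 and the closing sentence of 9.5.3.1.1.1 already use that test.

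The cost is one sentence in an amendment and a clarification to sites. The downside is a few more non-serious ocular AEs recorded. No treatment, visit or planned analysis changes.

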###### 9.5.3.1.1.2 Serious Adverse Event Definition

A treatment-emergent adverse event (TEAE), Baseline event, or suspected adverse reaction is considered serious if, in the view of either the Investigator or Sponsor, it results in any of the following outcomes:

- Death. This includes any death that occurs during the conduct of a clinical trial, including deaths that appear to be completely unrelated to the trial drug (e.g., due to car accident).
- Life-threatening adverse experience. An AE or suspected adverse reaction is considered life-threatening if, in the view of either the Investigator or the Sponsor, its occurrence places the patient at immediate risk of death. It does not include an AE or suspected adverse reaction that, had it occurred in a more severe form, might have caused death.

- Persistent or significant disability or incapacity.
- Inpatient hospitalization or prolongation of an existing hospitalization.
- Congenital anomaly or birth defect.
- Another medically important event that, according to appropriate medical judgment, may require medical or surgical intervention to prevent 1 of the outcomes listed above.

Surgical procedures or other therapeutic interventions themselves are not AEs, but the condition for which the surgery intervention is required is an AE and should be documented accordingly.

Elective surgeries that require hospitalization and treatment received at an emergency room or similar facility will not be considered as SAEs unless 1 of the definitions of an SAE listed above is met.

In addition, a hospitalization for planned procedures is not considered an AE unless the hospitalization becomes prolonged. An emergency room visit less than 24 hours in duration is not considered a hospitalization.

#### **9.5.3.1.1.3 Non-Serious Adverse Event Definition**

A non-serious AE includes any AE that is not included in the SAE definition.

